The primary objectives of the proposed Stage II study is to evaluate the effects of CBT in combination with tDCS in (1) improving pain and functionality, (2) reducing severity of opioid use disorders, and (3) reducing impairment in associated mental health areas (e.g., depression, anxiety, PTSD), with a novel focus on the role of sleep disturbance as a consequence, predictor and potential mediator of chronic pain. This study will also yield valuable data regarding the potential of CBT (with and without tDCS augmentation) to improve sleep in the context of chronic pain and opioid misuse. We will also determine the effects of treatment on neural activity in cognitive and limbic brain regions involved in pain regulation using functional magnetic resonance imaging (fMRI), and examine its relationship to sleep latency, total sleep time, sleep efficiency and opioid use severity. Secondary objectives are to evaluate acute lab-based pain markers and neural correlates of improvement in chronic pain using quantitative sensory testing. In order to accomplish this we are: using a manualized, evidence-based CBT intervention that is already widely-disseminated within the VA system; employing a randomized, between-groups, double-blind experimental design; and examining standardized, repeated, dependent measures of change in: (a) clinical outcomes such as pain, opioid and other substance use disorders (e.g., alcohol, illicit drugs, other prescription drugs), depression, anxiety, sleep and PTSD symptomatology; and (b) process variables such as participant satisfaction, quality of life and treatment retention.

The following specific aims are proposed:

Specific Aim 1: To compare the efficacy of CBT + real tDCS vs. CBT + sham tDCS, in reducing pain and improving sleep.

Specific Aim 2: To compare the efficacy of CBT + real tDCS vs. CBT + sham tDCS, and the potential mediating effects of sleep in reducing severity of prescription opiate use disorders, as well as impairment in associated areas (i.e., other substance use disorders, depression, anxiety, PTSD).

Specific Aim 3: To use fMRI to determine the effects of CBT (with and without tDCS) on the neural response to pain and its relationship with opiate use severity.

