In a recent study,⁴⁹ pain thresholds to electrical stimulation were assessed in 20 healthy individuals who received anodal tDCS. Four conditions of stimulation were compared: motor cortex (M1), DLPFC, occipital cortex, and sham. Results suggest that DLPFC tDCS can modulate the perception of pain via mechanisms independent of sensory perception.⁴⁹ An adjunctive study with 22 healthy individuals showed that anodal tDCS of the DLPFC (but not M1, occipital, or sham) decreased perception of unpleasantness and emotional discomfort/pain while subjects viewed aversive images.⁵⁰ While existing research shows analgesic effects of DLPFC stimulation in neuropathic pain, post-surgical pain, and laboratory-induced pain, and numerous studies support the efficacy of CBT for chronic pain, no published studies to date have combined these two intervention strategies. tDCS may prime and modulate prefrontal circuitry resulting in an enhanced capacity to tolerate and down-regulate the emotional component of pain experience, while CBT can teach the skills necessary to maintain these gains, thus creating a synergistic effect. By capitalizing on the effects of tDCS on prefrontal circuitry and combining them with CBT, we may achieve longer-term and more substantial pain reduction than with CBT alone. The present study represents a logical next step-forward in the development of non-pharmacologic interventions for the management of the chronic pain and commonly co-morbid conditions.

APPROACH

Overview: The proposed study is a Stage II double-blind, randomized controlled trial of the impact of combining tDCS with CBT in the treatment of CLBP in Veterans with co-morbid opioid use disorders. A repeated measures design with 2 intervention arms will be used: CBT + real tDCS vs. CBT + sham tDCS. Outcome measures allow us measurement of effects on pain, opioid use severity, as well as collateral mental and physical health (e.g., depression, other substance use, PTSD, quality of life).

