Alternately, the participant can provide BP documentation from a medical professional (within the past 6 weeks) and/or a study team member can view the participant's EPIC/CPRS record for a recent BP value. Self-report measures of pain, opiate misuse, depression, anxiety, PTSD, and sleep functioning will also be assessed at baseline and throughout the study.

During the baseline phase, eligible participants will have their cell phones registered into the *daily diary system* described below and will be given instructions on how to respond to daily queries regarding pain, mood, craving, etc. Patients without a cell phone will be provided a cell phone for use during the study. Actigraphy monitors will be provided for all participants for sophisticated measurement of sleep patterns that will allow investigators to examine (1) the impact of the investigational treatments on sleep patterns, (2) the temporal co-variation in sleep and pain, and (3) potential mediation effects of sleep on pain and opioid misuse. Eligible participants will then complete a 2-week baseline period during which daily diary assessments are obtained. During the 2-week baseline phase, patients will undergo structural and functional MRI scanning and QST procedures (described in more detail in the Study Interventions and Procedures section). These procedures will be repeated at the end of treatment.

Immediately following the baseline period, subjects will receive 11, 60-min sessions of manualized, individual CBT for pain delivered once a week over approximately 11 weeks. Therapy sessions may be delivered via doxy.me with the subject in an MUSC office at a standard desk using a laptop computer. Subjects will be randomized to receive real or sham tDCS during the therapy sessions. Within 3 weeks following completion of the CBT treatment, participants will repeat the neuroimaging and QST procedures. They will return at 1-, 3-, and 6-months post-treatment for follow-up visits. If participants are not able to return in person for the follow up visits, participants can complete the follow up assessments on REDCap, entered directly into the online portal to ensure security and prevent data loss.

Actigraphy measurement of sleep patterns will be recorded after the 2-week baseline period, post treatment, and at 1-, 3-, and 6-months post-treatment follow-up visits.

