Cognitive-Behavioral Therapy for Pain (CBT): All participants will receive 11, 60-min, manualized individual sessions of CBT for pain. We will use the therapy manual and accompanying patient workbook⁷², which were developed by [name] (Consultant; see *Letter of Support*) and are endorsed by the Department of Veterans Affairs and widely used nationally by the VA healthcare system. See Appendix A for the manuals. Examples of session topics include: education on chronic pain, diaphragmatic breathing and progressive muscle relaxation, automatic thoughts, cognitive restructuring, stress management, time-based pacing, pleasant activity scheduling, anger management, and sleep hygiene.

[figure not shown]
Therapist Training and Supervision: All therapists will be licensed Masters or Doctoral level clinicians with experience delivering CBT. During the lead-in/preparation phase of the study, therapists will receive extensive training in the CBT treatment protocol lead by Drs. [name], [name] and [name]. [name] is the developer of the CBT manual being employed in this study. Study therapists will complete four phases of training: (1) didactic review of intervention-specific theory; (2) manual review; (3) a 2-day training workshop and (4) subsequent completion of one to two pilot study case in which all sessions will be recorded and rated for therapist adherence and competency. Throughout the study, therapists will receive weekly supervision conducted by Drs. [name] and [name] focusing on manual adherence and competency, and clinical concerns about particular patients. If during the course of the study it is determined upon review of therapy sessions and supervisory sessions that a therapist is not competent or does not adhere sufficiently to the manual, the therapist will be replaced. The decision to replace a study therapist will be a conjoint decision made by Drs. [name], [name], and [name].

Adherence Ratings: Finally, to assure that the therapy is delivered in a manner consistent with manual guidelines, all therapy sessions will be recorded and randomly selected sessions (25% of therapy sessions) will be evaluated using methods developed by Hollon and colleagues⁷³ in the NIMH Collaborative Study. Interrater reliability on measures of adherence and competence between raters will be established.

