Neuroimaging Procedures: Functional MRI (fMRI) data will be acquired from all participants 1 week before and within 3 weeks of completion of the 11-session CBT protocol. The scans will be conducted at the MUSC Center for Biomedical Imaging, which is also designated as VA-approved space. High-resolution structural scans will be obtained at the beginning of each session using an inversion recovery 3D spoiled gradient echo (3DSPGR) sequence, 128 slices, matrix size: 256 x 256, field of view: 24 cm, section thickness: 1.5 mm with no gap between sections, giving an in-plane resolution of 0.94 mm. This sequence will be used for anatomic overlays of the functional data, for spatial normalization to a standard atlas, and subsequent voxel-based morphometry (beyond the scope of this proposal). Outside the scanner, participants will undergo a thermal method-of-limits procedure (aided by parameter estimation by sequential testing) to determine the temperature output required from the Medoc Pathway System to reliably produce a subjective NRS pain rating of 7/10. This temperature will be delivered in 12-second tonic blocks interspersed with 18-second rest/pain rating periods during the fMRI sequence. The data will be preprocessed in accordance with standard practice in our laboratory using SPM 8 (Wellcome Department of Cognitive Neurology, London, UK) and the average time courses from anatomically defined regions of interest (ROIs) extracted and analyzed using customized scripts (Matlab 6.5, Mathworks, Natick, MD).

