Hypothesis 2a: CBT + real tDCS will result in significantly greater reductions, as compared to CBT + sham tDCS, in COMM scores and opiate craving ratings (electronic diary) compared to CBT + sham tDCS. To test this hypothesis, time-series analysis of diary ratings of opiate cravings will be conducted and COMM total scores will be used as repeated measures variables using the HLM methods and co-variate strategies delineated above.

Hypothesis 2b: CBT + real tDCS will result in significantly greater reductions, as compared to CBT + sham tDCS, in depression (BDI-II), anxiety (BAI), PTSD (PCL-M) and sleep (PSQI). To test this hypothesis, total scores on the identified measurements will be used as repeated measures variables using the HLM methods and co-variate strategies delineated above.

Hypothesis 2c: Total sleep time will mediate the clinical benefits of combined CBT-tDCS on chronic pain. To test this, structural equation modeling (SEM) will be used to examine the amount of variance explained in clinical improvement related to tDCS+CBT with and without total sleep time entered into the temporally dynamic model.

Hypothesis 3a: At baseline, percent BOLD signal change in the left DLPFC during pain blocks will be inversely related to BOLD signal in the left insula, ACC, thalamus, caudate, putamen, and medial prefrontal cortex.

Hypothesis 3b: After treatment, percent BOLD signal change in the left DLPFC during pain blocks will be significantly greater in the CBT + real tDCS group as compared to CBT + sham tDCS.

Hypothesis 3c: Functional connectivity between the left DLPFC and insula and ACC after treatment will be greater in participants who receive CBT + real tDCS as compared to CBT + sham tDCS.

Hypothesis 3d: The change in functional connectivity will be correlated with changes in pain (BPI), opiate use severity (COMM), and total sleep time.

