For hypotheses 3a-3d, we will measure the following dependent variables: (1) percent change in BOLD signal in the left DLPFC as well as other limbic and executive regions of interest (ROIs) including the left and right insula, ACC, thalamus, caudate, putamen, and medial prefrontal cortex; and (2) functional connectivity (quantified as the average correlation coefficient between the ROIs) between the left DLPFC and the aforementioned ROIs will be used to test the hypothesis that CBT and tDCS have a synergistic effect on the neural adaptations in pain-control circuitry (i.e., insula and ACC). We will also investigate the functional connectivity with a negative control region (i.e., the primary visual cortex), which should not be differentially

modulated by either tDCS or CBT treatment. Group analyses will be performed using a random effects model (corrected, $p<0.01$ cluster level, $k= 25$, SPM 8).

Hypothesis 3e: Functional connectivity between the left DLPFC and insula and ACC after treatment will be greater in participants who receive CBT + real tDCS as compared to CBT + sham tDCS, and the change in functional connectivity will be correlated with changes in total sleep time.

HUMAN SUBJECTS RESEARCH

Protection of Human Subjects

Risks to Subjects

[name] is a licensed clinical psychologist with extensive training and experience in conducting human research. The Co-Is also have extensive experience in human research, and Drs. [name], [name], [name], [name], [name], [name], [name], and [name] have all completed the University of Miami computer-based CITI Human Subjects Research Education Course. All research activity, informed consents, and continuing reviews will be reviewed by MUSC's IRB in compliance with 45CFR46 before the research is started and continuing review will occur annually. The research staff will ensure that all information needed for the continuing review is at the IRB in accordance with IRB requirements.

Human Subjects Involvement and Characteristics

A total of 150 adults between the ages of 18 and 70 will be recruited over a 5-year period. The inclusion/exclusion criteria for the study are as follows:

Inclusion Criteria:

1. Ages 18 to 70.
2. United States Veteran or family member of a Veteran.
3. Able to provide informed consent and function at an intellectual level sufficient to allow accurate completion of the assessment instruments.
4. Subjects must be able to comprehend English.

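### The fMRI plan says it will test synergy between CBT and tDCS, but with CBT in both arms the trial can only estimate the effect of tDCS added to CBT

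*Combined protocol and SAP*

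**What the plan says.** The design is set out consistently. The Approach overview states: "A repeated measures design with 2 intervention arms will be used: CBT + real tDCS vs. CBT + sham tDCS". The section on CBT for pain adds: "All participants will receive 11, 60-min, manualized individual sessions of CBT for pain". General Procedures names what is allocated at random: "Subjects will be randomized to receive real or sham tDCS during the therapy sessions". Under Neuroimaging Procedures there are two scans: "Functional MRI (fMRI) data will be acquired from all participants 1 week before and within 3 weeks of completion of the 11-session CBT protocol".

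The imaging hypotheses that compare arms follow that design. Hypothesis 3c, for example, expects that post-treatment connectivity "will be greater in participants who receive CBT + real tDCS as compared to CBT + sham tDCS".

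The paragraph on dependent variables for hypotheses 3a to 3d goes further. It says that connectivity between the left DLPFC and the other regions will be used to "test the hypothesis that CBT and tDCS have a synergistic effect on the neural adaptations in pain-control circuitry". It also describes the negative-control region as one that should not be differentially "modulated by either tDCS or CBT treatment".

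Two background passages use the same idea. Specific Aims notes that no study has directly examined synergy between the two treatments and presents this study as addressing a gap. The Significance text on brain stimulation for pain and addiction ends its rationale on a synergistic effect. Specific Aim 3 does not mention synergy. Its stated purpose is "To use fMRI to determine the effects of CBT (with and without tDCS) on the neural response to pain".

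**The concern.** Synergy is a statement about interaction: tDCS does more in the presence of CBT than in its absence. To test it, one must know what tDCS does without CBT, and no participant in this trial goes without CBT. The plan therefore names a hypothesis that its only randomized contrast cannot address.

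At stake is what a positive result may be said to show. As the plan is worded, higher connectivity under CBT + real tDCS would count as support for synergy, although the same result is expected if the two treatments simply add. A related, smaller issue is the effect of CBT itself. CBT is constant across arms, so any change after CBT is seen only as a before-after difference.

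**Working it through.** **Plan's own figure.** There is none to reproduce. The Power section gives no interaction effect. Its fMRI figure rests on an effect of 1.8 for pain minus rest, which is neither a between-arm nor an interaction effect.

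**Step 1: what the arms estimate.** Let m be the mean outcome with neither active treatment, C the effect of CBT alone, T the effect of tDCS alone, and I the interaction (synergy if I > 0). The four possible cells are:

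- neither: m
- CBT + sham: m + C
- tDCS without CBT: m + T
- CBT + real tDCS: m + C + T + I

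The trial observes the second and fourth. Their difference is (m + C + T + I) − (m + C) = T + I.

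**Step 2: put numbers in.** In SD units:

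| T | I | Contrast T + I |
|---|---|---|
| 0.5 | 0 | 0.5 |
| 0.25 | 0.25 | 0.5 |
| 0 | 0.5 | 0.5 |
| 0.7 | −0.2 | 0.5 |

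Additive, partly synergistic, wholly synergistic and antagonistic truths all give the same expected contrast. The value 0.5 is borrowed from the Power section, where it is the assumed effect on clinical pain. The documents give no between-arm effect for connectivity, so the table illustrates the algebra and does not forecast the imaging result.

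**Step 3: rank check.**

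- Two arms, parameters m, C, T, I: rank 2 of 4.
- Two arms with pre and post scans, parameters intercept, time, C×time, T×time, I×time: rank 3 of 5. CBT is aliased with time, and the interaction with tDCS.
- Two arms plus a tDCS-without-CBT arm: three means for four parameters, so rank 3 of 4. I is still not identified.
- Full 2×2 factorial: rank 4 of 4.

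Separating T from I therefore needs both missing cells: real tDCS without CBT, and sham (or no) tDCS without CBT.

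**Step 4: a planned success would not discriminate.** The Power section takes d = 0.5 from the literature on tDCS for chronic pain and powers the trial at d = 0.5. Assume that this literature reflects tDCS given without CBT. The Significance section's remark that no published study has combined the two points that way. Then T = 0.5, and pure additivity (I = 0) predicts a clinical arm contrast of 0.5, which is the size planned for. The same algebra governs the connectivity contrast.

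**Step 5: what a real synergy test would ask for (illustration only).** Assume a 2×2 factorial with the same total of 150 (37.5 per cell), SD 1 and no dropout. SE of the interaction = √(4/37.5) = 0.327.

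| Interaction (SD) | Power, α = .05 | Power, α = .01 | Total N for 80% power, α = .05 |
|---|---|---|---|
| 0.25 | 0.12 | 0.04 | 2012 |
| 0.5 | 0.33 | 0.15 | 504 |
| 0.75 | 0.63 | 0.39 | 224 |
| 1.0 | 0.86 | 0.69 | 128 |

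The documents give no interaction size, so this is a range. Unless the interaction is large, adding the missing cells at the present size would not give an adequate test.

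**The case against.** The best reply is that the documents mostly ask the right question. They repeatedly speak of tDCS augmenting CBT, and the Significance section sets the benchmark as more pain reduction than CBT alone. On this view, synergistic is a loose word for complementary mechanisms, the imaging outcomes are not among the primary outcomes listed under Data Management and Analysis, and rewording changes no contrast, model or sample size. Most of this stands, and it limits the point to wording. It does not remove it. The synergy clause is in the analysis section as a hypothesis to be tested, and Specific Aims presents the study against a gap described as synergy.

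A reader might infer several stronger things that the documents do not support:

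- *That the main comparison is invalid.* It is not. Real versus sham tDCS given CBT is a proper randomized contrast, and Aims 1 and 2, hypotheses 3b and 3c, and the first half of 3e all use it.
- *That Aim 3 also claims to test synergy, or that a faulty test of CBT is planned.* Aim 3 never mentions synergy, and comparing CBT with and without tDCS can be read as comparing the two arms. No listed fMRI hypothesis tests pre-post change in the sham arm: 3a is a baseline association, and 3d and the second half of 3e are correlations of change.
- *That power for synergy is zero.* The right term is non-identifiable. When two truths give the same data distribution, a test's power equals its size.
- *That a tDCS-only arm would solve it.* Step 3 shows that it would not.
- *That the results will be reported as synergy.* That is a prediction. The documents show only that the wording allows it.

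**Conclusion.** The point holds as a fault of wording in the analysis plan. The stated test of synergy is one that the design cannot provide at any sample size, because the arm contrast is T + I and nothing observed separates the two terms. This rests on three facts that the documents state plainly (two arms, CBT for everyone, randomization of tDCS only) and on reading synergy in its usual sense of interaction. If the sponsor means only an add-on effect, the test is valid and the word is wrong.

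The remark about CBT is a lesser clarification. Change within CBT + sham can be described, but it cannot be separated from time, repeat scanning, sham response, concurrent care or regression to the mean. The last is plausible because entry requires minimum pain and COMM scores.

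**What to change.** - In the dependent-variables paragraph for hypotheses 3a to 3d, replace the synergy clause with: *tDCS added to CBT has an effect beyond CBT with sham tDCS*.
- Bring the gap statement in Specific Aims and the closing rationale in the Significance text on brain stimulation into line. Synergy may stay as a motivating idea if it is marked as not tested here.
- As a lesser clarification, state in Aim 3, and in the Specific Aims sentence on CBT's potential to improve sleep, that the estimand is the added effect of real versus sham tDCS given CBT, and that change within CBT + sham is uncontrolled pre-post change.
- State that no conclusion about synergy or about the efficacy of CBT will be drawn from this trial.

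These are text changes only, best made before results are reported. No arm, participant, visit or analysis is added. The cost is a narrower permitted claim.

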fMRI power to detect effects for planned contrasts was estimated as function of N, mean difference in percent signal change between block/conditions (μ_D), within-subject variability over time (σ_W), and between subject variability (σ_B) based on previous work conducted by our group. The effect size for our previously employed pain minus rest contrast was 1.8. Thus, power (1- β) reaches .80 with only 12 participants per group (two-tailed, alpha=.01). The present study is therefore well-powered to identify significant connectivity and activation patterns using the pain-rest block paradigm and functional connectivity methods proposed.

Hypotheses: The hypotheses and statistical approaches for testing each hypothesis is as follows:

Hypothesis 1a: CBT + real tDCS will result in significantly greater improvements, as compared to CBT + sham tDCS, in average daily pain (electronic diary), pain unpleasantness (electronic diary) and functional impairment due to pain (BPI). To test this hypothesis, time-series analysis of diary average pain and pain-unpleasantness ratings will be conducted and BPI total scores will be used as repeated measures variables using the HLM methods and model co-variate strategies delineated above.

Hypothesis 1b: CBT + real tDCS will result in significantly greater improvement, as compared to CBT + sham tDCS, in sleep latency, total sleep time and sleep efficiency. To test this hypothesis, time-series analysis of actigraphy sleep latency, total sleep time and sleep efficiency values will be used as repeated measures variables using the HLM methods and model co-variate strategies delineated above.

Hypothesis 1c: Sleep latency, total sleep time, and sleep efficiency will improve significantly after the manualized CBT module devoted to sleep hygiene compared to other CBT modules. To test this hypothesis, interrupted time-series analysis (via HLM) will be conducted with the "Sleep Hygiene" CBT module established as the temporal demarcation point.

Hypothesis 1d: Time-series data representing sleep latency, total sleep time and sleep efficiency *improvements will lead* any observed *improvements* in pain and functioning consistent with emerging data on the temporal relationship between sleep and pain.⁷⁹ To test this hypothesis, lead-lag analysis of key time-series variables (sleep latency, total sleep time and sleep efficiency, pain and functional impairment due to pain) will be conducted.

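### The only group rule stated for the fMRI hypotheses is a voxel-cluster threshold, which does not fit outcomes defined as one number per region or region pair

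*Combined protocol and SAP*

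**What the plan says.** All references are to the combined protocol and SAP.

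- **Outcomes.** The paragraph after Hypothesis 3d lists two dependent variables. The first is "percent change in BOLD signal in the left DLPFC as well as other limbic and executive regions of interest (ROIs". The second is "functional connectivity (quantified as the average correlation coefficient between the ROIs". Neuroimaging Procedures describes the same data handling: "the average time courses from anatomically defined regions of interest (ROIs) extracted and analyzed using customized scripts".
- **Hypotheses.** 3b names one region after treatment: "percent BOLD signal change in the left DLPFC during pain blocks will be significantly greater in the CBT + real tDCS group", compared with sham. 3c names the connections of the left DLPFC with the insula and the ACC. 3e repeats the arm comparison of 3c and adds a correlation with change in total sleep time.
- **Group rule.** The paragraph after 3d closes with "Group analyses will be performed using a random effects model (corrected, $p<0.01$ cluster level", with k = 25 in SPM 8. It gives no cluster-forming threshold, search volume or small-volume correction. Its lead-in covers 3a-3d. Hypothesis 3e is printed after it and has no test of its own.
- **Alpha.** The fMRI part of the Power section uses a two-tailed .01. Data Management and Analysis sets .05 for primary hypotheses and lists pain, opioid use severity and sleep as the primary outcomes, without fMRI.

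**The concern.** An average over a region, or a correlation between two regional time courses, is a single value per person. It has no voxels, so it has no cluster and no extent. The stated rule can be applied only if the stated outcome is replaced by a voxel map, and that changes the null hypothesis. The null for 3b should be equal mean left-DLPFC signal change in the two arms. The cluster null is that no supra-threshold cluster of the required size exists anywhere in the searched volume. The two tests can disagree in either direction.

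What is at stake is the arm comparison in Aim 3. As written, 3c and the matching part of 3e have no group test that can be carried out on their defined outcome. 3b could be decided after the data are seen either by a cluster map with open settings or by a regional test that nobody has specified.

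**Working it through.** **1. Does the rule fit the outcomes?** This step needs no arithmetic.

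| Hypothesis | Outcome per participant, as defined | Can the cluster rule give a p-value for it? |
|---|---|---|
| 3b | One left-DLPFC percent signal change | Only if a voxel map replaces the regional value |
| 3c | One correlation per connection (DLPFC-insula, DLPFC-ACC) | No. A voxelwise seed map would be a different outcome |
| 3e, arm comparison | As 3c | No, and the rule's lead-in does not cover 3e |

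**2. The plan's own fMRI power figure.** The Power section gives .80 with 12 per group, effect size 1.8 and two-tailed alpha .01. For a two-sample comparison, the noncentrality is 1.8 × √(12/2) = 4.41. The normal approximation gives Φ(4.41 − 2.576) = Φ(1.83) = .97, and the noncentral t gives .93. The .80 is not reproduced, but it errs on the cautious side for its own inputs. It does not help here, because the plan says "The effect size for our previously employed pain minus rest contrast was 1.8". That is not a real-versus-sham difference, and the calculation has no cluster step.

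**3. Power of a one-number test of 3b.** Inputs from the plan are 75 per arm and scans in all participants. The documents give no real-versus-sham BOLD effect, so d = .5 (the plan's clinical effect size) is an assumption. Noncentrality is .5 × √(75/2) = 3.06.

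- Alpha .05: Φ(3.06 − 1.96) = .86 (t: .86).
- Alpha .01: Φ(3.06 − 2.576) = .69 (t: .67).
- Range by t: d = .3 gives .45 at alpha .05 and .22 at .01; d = .8 gives .998 and .99.

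Dropout before the second scan would lower all of these.

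**4. Power of the cluster rule, by simulation.** None of these settings is in the documents: 3 mm voxels, 8 mm smoothness, about 55,700 brain voxels, a 619-voxel DLPFC region, two-sided family-wise error .01, and 20% to 60% of voxel noise variance shared across the region. The effect is uniform over the region, with regional d = .5.

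| Search volume | Forming p<.001 | Forming p<.01 |
|---|---|---|
| Whole brain | .24 to .57 | .46 to .81 |
| DLPFC region only | .45 to .67 | .54 to .68 |

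A second simulation used 6-10 mm smoothness, regions of about 300-900 voxels, 30-80% shared variance and a one-sided cluster test. For a whole-brain search it gave .25 to .63 and .36 to .86. Against the regional test at the same .01 level (.67), these results run from a clear loss to a gain of 19 points (.86 − .67).

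**5. Effect in only part of the region.** Voxel d = .5, whole-brain search, forming p<.001, 20% to 40% shared variance, regional mean tested at alpha .05:

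- 13% of the region active: cluster .57 to .59, regional mean .09 to .12.
- 41% active: cluster .84 to .92, regional mean .46 to .69.

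This reversal also depends on an unstated setting. At forming p<.01 the critical whole-brain extent is about 103 voxels, against 32 at p<.001. An effect filling the 13% patch (81 voxels) is then found with power of only .04 to .05, even when it is strong enough to give a regional d of .5.

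**The case against.** The strongest reply is that the plan does describe a regional route. Time courses are extracted and analysed in Matlab, and nowhere does the text say that the SPM threshold alone decides 3b or 3c. This stands in part. It would be wrong to infer that regional analysis is absent; what is absent is its group test. The scripts come with no model, arm comparison, alpha or multiplicity rule, so they do not supply the missing test, and the one rule that is stated does not suit the outcomes.

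A reader might also infer that the cluster rule costs a known and large amount of power, for example by setting .86 for a regional test against .25 to .63 for a whole-brain cluster test. The documents do not support that. The search volume, forming threshold, smoothness and spread of the effect are all unstated, and the hypotheses name regions, so a restricted search is equally open. The comparison also mixes alphas: .05 is set for primary hypotheses, whose listed outcomes exclude fMRI, while the fMRI power statement uses .01. Of any gap measured from .86, 19 points (.86 − .67) come from the change of alpha and not from the type of test.

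**Conclusion.** The mismatch holds on the text alone. The stated group rule cannot decide 3c or the arm comparison in 3e on the outcome as defined, and for 3b it tests a different null over an unstated volume. This rests on no simulation.

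The effect on power is conditional. The rule may cost power for 3b if the search is whole-brain and the effect spans the region. The loss shrinks, vanishes or reverses with a laxer forming threshold, a search limited to the region, or an effect in part of it. No fixed loss should be quoted, and a negative Aim 3 result cannot be predicted from the rule. The regional-test figures of .86 and .67 rest on an assumed d of .5 and complete scans in 75 per arm.

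The point concerns Aim 3 only. It should be settled before the fMRI data are analysed.

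**What to change.** In the paragraph after Hypothesis 3d:

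- **3b:** decide by a linear model of each participant's post-treatment left-DLPFC percent signal change on arm, adjusted for the baseline scan value.
- **3c and the arm comparison in 3e:** use the same model on Fisher-z left-DLPFC-insula and left-DLPFC-ACC correlations, with Holm across the connections tested. State whether left and right insula are averaged or counted separately.
- **Alpha:** state one two-sided level for these tests, and reconcile the .01 in the fMRI power text with the .05 that Data Management and Analysis sets for primary hypotheses.
- **Cluster analysis:** keep it as an exploratory map, with its search volume and forming threshold stated, and say that it does not decide 3b, 3c or 3e.

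The cost is wording only, since the regional values are already to be extracted. The drawback is that an effect confined to a small part of the region is diluted in the average, though the exploratory map may still show it. The correlational hypotheses (3a, 3d and the second half of 3e) also lack a named test; this change does not supply one.
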